| N: Baseline scans must be done <4 weeks prior to randomization. Tumor measurement will be performed with contrast CT chest/abdomen/pelvis. Non-contrast CT chest/abdomen/pelvis or CT Chest and MRI Abdomen/pelvis will be performed in subjects with contraindications or intolerance to contrast dye. For the first on-treatment scan, this should be done approximately 8 weeks from the start of treatment (not from the date of the pre-treatment baseline scan). Imaging will be repeated every 8 weeks, irrespective of dosing schedule or treatment delays. For the End of Treatment visit, scans do not need to be repeated if a scan has been performed within 8 weeks. For patients removed from study treatment for reasons other than progression, scans are to continue every 8 weeks until progression. |                                    |                      |         |        |        |         |       |        |                    |        |       |  |        |        |
| O: CA19-9 does not need to be repeated in the event that the screening lab draw show that the patient's tumor does not secrete CA19-9.   |                                    |                      |         |        |        |         |       |        |                    |        |       |  |        |        |
| P: Only for subjects with tumor that in the opinion of the study treatment team is safely accessible for biopsy. See Section 5.5.2 for the order of the tumor cores to be collected. The baseline biopsy is to be done after randomization but before C1D1.  |                                    |                      |         |        |        |         |       |        |                    |        |       |  |        |        |
| Q: Blood collection will be collected at baseline, C1D21, and Week 12 (end of Cycle 3). Pre-treatment baseline EDTA and Streck tube draws should only be drawn on enrolled patients and can be drawn anytime between time of enrollment and prior to start of treatment. These samples must be collected only Monday - Thursday and shipped overnight same day. See Section 5.1 for more details.  |                                    |                      |         |        |        |         |       |        |                    |        |       |  |        |        |
| R: D1 of Cycles 1-6, 9, 12; pharmacokinetic and immunogenicity: pharmacokinetic blood draws will be performed pre-infusion and 30 minutes after the end of infusion of CDX-1127 (varilumab), which will be administered after atezolizumab and D15 of Cycle 1 and 2. See Section 5.1 for more details.   |                                    |                      |         |        |        |         |       |        |                    |        |       |  |        |        |
| S: End of Treatment evaluations will be completed no more than 30 days after the last dose of all study drugs and prior to start of next line systemic therapy.  |                                    |                      |         |        |        |         |       |        |                    |        |       |  |        |        |
| T: Patients receiving cobimetinib ( study arm A only ). Labs during treatment may be collected within a window of up to 3 days prior to dosing days.  |                                    |                      |         |        |        |         |       |        |                    |        |       |  |        |        |
| U: Evaluation of LV function by either echocardiogram (ECHO) or multiple-gated acquisition (MUGA) at baseline ( all patients ), 1 month after first dose ( study arm A only ), then every 3 months while on cobimetinib (visit window $+/-7$ days); ( study arm A only ).   |                                    |                      |         |        |        |         |       |        |                    |        |       |  |        |        |
| V: Ophthalmologic examination at baseline ( all patients , within 4 weeks prior to randomization ), then every 2 months for 1 year ( study arm A only ), then every 6 months while on cobimetinib (visit window $+/-14$ days); ( study arm A only ). Eye exam should include retinal exam, slit lamp exam, and visual fields (preferably Goldmann Visual Field if available) for evidence of retinal pathology and other abnormalities. Alternatives to Goldmann Visual field tests such as Humphrey and Octopus visual field tests/machines are acceptable. Alternatives to checking visual acuity with Landolt chart such as ETDRS and documentation of Snellen equivalent are acceptable.   |                                    |                      |         |        |        |         |       |        |                    |        |       |  |        |        |
| W: Adverse events will be assessed at least 30 days after the last dose of either study agent. For patients removed due to unacceptable toxicity, they will be followed until resolution of the adverse event.   |                                    |                      |         |        |        |         |       |        |                    |        |       |  |        |        |
| X: End of Cycle 3 only (including up to prior to starting treatment on C4D1).  |                                    |                      |         |        |        |         |       |        |                    |        |       |  |        |        |
| Y: Before the on-study biopsy.   |                                    |                      |         |        |        |         |       |        |                    |        |       |  |        |        |
| Z: Patients receiving cobimetinib ( study arm A only ). EKG will be performed after randomization but before C1D1, at C1D15, monthly during the first 3 months, and then every 3 months thereafter or more often as clinically indicated.   |                                    |                      |         |        |        |         |       |        |                    |        |       |  |        |        |
| AA: Day 0 = time period after randomization up until C1D1 of treatment. Baseline research blood draws (EDTA and Streck tubes) and baseline study tissue biopsies should take place during this period (after patient has completed enrollment and prior to start of therapy).  |                                    |                      |         |        |        |         |       |        |                    |        |       |  |        |        |

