### 4.4 General Guidelines

Following registration, patients should begin protocol treatment within 7 days. Issues that would cause treatment delays should be discussed with the Principal Investigator. If a patient does not receive protocol therapy following registration, the patient’s registration on the study may be canceled. The Study Coordinator should be notified of cancellations as soon as possible.

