##### Progression Free Survival (PFS):

PFS is defined as the duration of time from date of randomization to time of progression or death. This analysis is intent-to-treat including all randomized patients. Patients who come off of study treatment for clinical progression without radiographic progression (i.e. clinical progression) will be coded as progression for the analysis, and the date of progression is the date of clinical progression. Due to the rapid progression of the disease in the majority of patients, little loss to follow up is expected, but subjects who are lost to follow-up as of the data analysis cutoff date will be right-censored. The censoring date will be determined from the date the subject was last evaluated for progression. PFS within each treatment arm will be summarized descriptively using Kaplan-Meier plots, and compared between arms using log-rank tests.

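### Scans are timed from first dose while co-primary PFS runs from randomisation: a start lag in one arm, if it occurred, could bias the log-rank test, and patients who never start have no date to count from

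*Combined protocol and SAP*

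**What the plan says.** Section 9.1, repeated in 12.1.6, fixes the PFS clock: "PFS is defined as the duration of time from date of randomization to time of progression or death". It fixes the analysis set ("This analysis is intent-to-treat including all randomized patients") and the test ("compared between arms using log-rank tests").

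The scan clock is in footnote N of the Study Calendar (section 11): "first on-treatment scan, this should be done approximately 8 weeks from the start of treatment". After that, "Imaging will be repeated every 8 weeks, irrespective of dosing schedule or treatment delays". Scans for patients taken off treatment without progression also continue every 8 weeks.

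The interval between the two clocks is governed by section 4.4: "Following registration, patients should begin protocol treatment within 7 days". Expected delays are to be discussed with the Principal Investigator, so the limit is a soft one. Under section 4.3.2, registration takes place when the patient is ready to be randomised.

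Three items bear on Arm A only. Footnote Z says "EKG will be performed after randomization but before C1D1". The Arm A regimen table in section 6.1 has cobimetinib taken before arrival on infusion days. Section 8.1.4.1 lets sites order the agents once the patient is enrolled.

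Section 9.2 compares PFS only if both arms meet the response criterion. The test uses 55 events at one-sided 0.10.

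**The concern.** Radiographic progression can be dated only on a scan day, so PFS events bunch at about 8, 16 and 24 weeks after first dose. Measured from randomisation, each patient's bunch is displaced by that patient's own start delay. If the delays have the same distribution in both arms, the displacement is noise. If one arm starts later on average, its events tend to follow the other arm's at every wave, and a rank test counts that ordering as longer PFS although tumour control is identical.

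What is at stake is the only planned randomised efficacy comparison. The trial is open-label, and the Arm A steps listed above would all push in the direction that favours the triplet.

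A second, smaller point is that a randomised patient who is never dosed belongs to the PFS analysis set, but footnote N gives no date from which to count that patient's scans.

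**Working it through.** **The plan's own figure.** With 1:1 allocation, events = 4(z₀.₉₀ + z₀.₉₀)² / (ln 0.5)² = 4 × (1.2816 + 1.2816)² / 0.4805 = 54.7, so 55. Power with 55 events is 0.901. The stated 55 events and 90% are reproduced.

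**Mechanism by hand, with complete separation.** A 3.5-month median is 3.5 × 30.4375 = 106.5 days. The chance of progressing within one 56-day interval is 1 − 2^(−56/106.5) = 0.305. Take identical outcomes in both arms: of 32 per arm, about 10, 7 and 5 progress at waves 1, 2 and 3. Let every Arm A scan fall just after every Arm B scan.

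| Wave | At risk per arm | Expected Arm A events | Observed | Difference |
|---|---|---|---|---|
| 1 | 32 | 10 × 32/64 + 10 × 32/54 = 10.93 | 10 | 0.93 |
| 2 | 22 | 7 × 22/44 + 7 × 22/37 = 7.66 | 7 | 0.66 |
| 3 | 15 | 5 × 15/30 + 5 × 15/25 = 5.50 | 5 | 0.50 |

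The differences sum to 2.09. The hypergeometric variances sum to 2.14 + 2.00 + 1.51 + 1.41 + 1.08 + 1.00 = 9.14, so z = 2.09/√9.14 = 0.69 towards the triplet. Taken as a shift in the mean of the statistic, P(Z > 1.28 − 0.69) is about 0.28 instead of 0.10. Real scan dates overlap, which reduces this.

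**Simulation under no true effect.** From the plan: 32 per arm, 3.5-month median in both arms, 56-day scans, analysis at the 55th event, one-sided 0.10. Assumed, because the documents give no values: start delay of 0 to 7 days at random in both arms, an added Arm A lag, scan scatter, and the share of events dated exactly (deaths and clinical progression).

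| Setting | Lag 2 days | Lag 3 days | Lag 5 days |
|---|---|---|---|
| 30% exact dates, ±3 days scatter | 0.119 | 0.138 | 0.142 |
| 30% exact dates, ±7 days scatter | 0.130 | 0.116 | 0.123 |
| All events scan-dated, ±3 days | 0.14 | 0.17 | 0.20 |
| All events scan-dated, ±7 days | 0.13 | 0.13 | 0.17 |
| All events on exact scan days | 0.16 | 0.19 | 0.24 |

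The first two rows are from 3,000 runs (standard error about 0.006) and the rest from 6,000 (about 0.005). A separate repeat of the last row gave 0.16 to 0.23. A separately coded run with a 3-day lag, ±3 days scatter and 30% exact dates gave 0.145. A 1-day lag with 30% exact dates gave 0.108 (±3 days) and 0.104 (±7 days), which cannot be told from 0.10.

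If all patients within an arm share one start delay, separation is sharper. With exact scan days and every event scan-dated, the error is then 0.32 for a 3-day and 0.27 for a 7-day difference. This is a stylised extreme, close to the hand calculation.

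**Controls.** Delays of 0 to 7 days with the same distribution in both arms give 0.104. With scans counted from randomisation, a 7-day versus 0-day start difference gives 0.101 (exact scan days, all events scan-dated) and 0.103 (±3 days, 30% exact).

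**Power at HR 0.5, 30% exact dates.** Equal starts give 0.88 to 0.89, the triplet 3 to 7 days later 0.91 to 0.94, and the doublet 3 to 7 days later 0.85 to 0.88.

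**Censoring.** The plan states that "The censoring date will be determined from the date the subject was last evaluated for progression". Censoring event-free patients at the last scan, rather than at the cut-off, moves the error slightly upwards and does not change the reading.

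**Patients who never start.** Footnote N counts from a date they do not have, and its off-treatment sentence covers only patients removed from treatment. Section 6.5 asks for disease-status monitoring at least every three months but names no imaging. Section 12.1 gives 8-weekly re-evaluation without a start date. Section 4.4 allows cancellation of the registration, which fits poorly with a PFS set of all randomised patients.

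**The case against.** A reader might infer that the PFS test is biased as planned. The documents do not support that. No section says that one arm starts later, and the scan rule is the same in both. Several steps before Cycle 1 Day 1 are shared: the baseline biopsy where accessible, research blood draws limited to Monday to Thursday, and ordering of both antibodies. An EKG can be done alongside these. A 5-day lag added to a 0 to 7 day delay puts Arm A at 5 to 12 days, mostly beyond the section 4.4 window. Deaths and clinical progressions carry their own dates, and footnote N says only approximately 8 weeks, so exact scan days for every event are unrealistic. All of this stands. It lowers the likely size and makes the bias conditional; it does not remove the mechanism.

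The response gate also matters. At a true response rate of 5%, each arm passes with probability 0.072, so two independent arms both pass with probability 0.072² = 0.005. The error rates above apply only once both have passed. At 20% that probability is 0.901² = 0.81, so the comparison would usually be run if both regimens are active.

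A reader might also infer that never-treated patients have no follow-up at all. That is wrong: sections 6.5 and 12.1 still apply, and deaths count as events. What stands is only that their 8-week clock has no start date.

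Finally, footnote N already keeps imaging fixed through dose delays, which deals with toxicity holds in the triplet arm. Only the starting anchor is open.

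**Conclusion.** The mismatch between the two clocks is plain in the text. Its effect is a risk and not a demonstrated bias: it needs a systematic difference between arms in time from randomisation to first dose, which the documents neither show nor rule out. Assuming Arm A lags by 2 to 5 days, 30% of events are dated exactly and scans scatter by ±3 to ±7 days, the one-sided type I error is about 0.11 to 0.14 against 0.10. If every event fell on an exact scan day, it would reach about 0.23 under the same random start delays. Equal delays give no inflation. The rates are conditional on both arms meeting the response criterion. For randomised patients who never start, the gap is a missing start date for the 8-week schedule. This is a modest exposure that can be removed almost for free.

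**What to change.** In footnote N, and by reference in section 12.1, state that tumour assessments take place every 8 weeks counted from the date of randomisation in both arms, including patients who start late or never start. Add that the 4-week confirmatory scan in section 12.1 does not move this schedule.

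The cost is a sentence or two. The first scan will usually fall up to about a week earlier relative to first dose. Section 9.1 counts a response at any time during the study, so an earlier first look does not by itself lose a later response. Treated patients have no extra scans, and the 55 events do not change. Patients who never start would be scanned on a defined schedule, which the all-randomised PFS analysis needs.

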## 12. MEASUREMENT OF EFFECT

### 12.1 Antitumor Effect – Solid Tumors

For the purposes of this study, patients should be re-evaluated for response every 8 weeks. In addition to a baseline scan, confirmatory scans should also be obtained 4 weeks following initial documentation of objective response.

Response and progression will be evaluated in this study using the new international criteria proposed by the revised Response Evaluation Criteria in Solid Tumors (RECIST) guideline (version 1.1) [Eur J Ca 45:228-247, 2009]. Changes in the largest diameter (unidimensional measurement) of the tumor lesions and the shortest diameter in the case of malignant lymph nodes are used in the RECIST criteria.

#### 12.1.1 Definitions

Evaluable for Toxicity. All patients will be evaluable for toxicity from the time of their first treatment with atezolizumab, cobimetinib, and CDX-1127 (varlilumab).

Evaluable for Objective Response. Only those patients who have measurable disease present at baseline, have received at least one cycle of therapy, and have had their disease re-evaluated will be considered evaluable for response. These patients will have their response classified according to the definitions stated below. (Note: Patients who exhibit objective disease progression prior to the end of cycle 1 will also be considered evaluable.)

Evaluable Non-Target Disease Response. Patients who have lesions present at baseline that are evaluable but do not meet the definitions of measurable disease, have received at least one cycle of therapy, and have had their disease re-evaluated will be considered evaluable for non-target disease. The response assessment is based on the presence, absence, or unequivocal progression of the lesions.

#### 12.1.2 Disease Parameters

Measurable Disease. Measurable lesions are defined as those that can be accurately measured in at least one dimension (longest diameter to be recorded) as  $\geq 20$  mm ( $\geq 2$  cm) by chest x-ray or as  $\geq 10$  mm ( $\geq 1$  cm) with CT scan, MRI, or calipers by clinical exam. All tumor measurements must be recorded in millimeters (or decimal fractions of centimeters).

Note: Tumor lesions that are situated in a previously irradiated area might or might not be considered measurable. *If the investigator thinks it appropriate to include them, the conditions under which such lesions should be considered must be defined in the protocol.*

Malignant Lymph Nodes. To be considered pathologically enlarged and measurable, a lymph node must be  $\geq 15$  mm ( $\geq 1.5$  cm) in short axis when assessed by CT scan (CT scan slice thickness recommended to be no greater than 5 mm [0.5 cm]). At baseline and in follow-up, only the short axis will be measured and followed.

**Non-Measurable Disease.** All other lesions (or sites of disease), including small lesions (longest diameter  $<10$  mm [ $<1$  cm] or pathological lymph nodes with  $\geq 10$  to  $<15$  mm [ $\geq 1$  to  $<1.5$  cm] short axis), are considered non-measurable disease. Bone lesions, leptomeningeal disease, ascites, pleural/pericardial effusions, lymphangitis cutis/pulmonitis, inflammatory breast disease, and abdominal masses (not followed by CT or MRI), are considered as non-measurable.

Note: Cystic lesions that meet the criteria for radiographically defined simple cysts should not be considered as malignant lesions (neither measurable nor non-measurable) since they are, by definition, simple cysts.

‘Cystic lesions’ thought to represent cystic metastases can be considered as measurable lesions, if they meet the definition of measurability described above. However, if non-cystic lesions are present in the same patient, these are preferred for selection as target lesions.

**Target Lesions.** All measurable lesions up to a maximum of 2 lesions per organ and 5 lesions in total, representative of all involved organs, should be identified as **target lesions** and recorded and measured at baseline. Target lesions should be selected on the basis of their size (lesions with the longest diameter), be representative of all involved organs, but in addition should be those that lend themselves to reproducible repeated measurements. It may be the case that, on occasion, the largest lesion does not lend itself to reproducible measurement in which circumstance the next largest lesion which can be measured reproducibly should be selected. A sum of the diameters (longest for non-nodal lesions, short axis for nodal lesions) for all target lesions will be calculated and reported as the baseline sum diameters. If lymph nodes are to be included in the sum, then only the short axis is added into the sum. The baseline sum diameters will be used as reference to further characterize any objective tumor regression in the measurable dimension of the disease.

**Non-Target Lesions.** All other lesions (or sites of disease) including any measurable lesions over and above the 5 target lesions should be identified as **non-target lesions** and should also be recorded at baseline. Measurements of these lesions are not required, but the presence, absence, or in rare cases unequivocal progression of each should be noted throughout follow-up.

#### 12.1.3 Methods for Evaluation of Measurable Disease

All measurements should be taken and recorded in metric notation using a ruler or calipers. All baseline evaluations should be performed as closely as possible to the beginning of treatment and never more than 4 weeks before the beginning of the treatment.

The same method of assessment and the same technique should be used to characterize each identified and reported lesion at baseline and during follow-up. Imaging-based evaluation is preferred to evaluation by clinical examination unless the lesion(s) being followed cannot be imaged but are assessable by clinical exam.

**Clinical Lesions.** Clinical lesions will only be considered measurable when they are superficial (e.g., skin nodules and palpable lymph nodes) and  $\geq 10$  mm ( $\geq 1$  cm) diameter as assessed using

calipers (e.g., skin nodules). In the case of skin lesions, documentation by color photography, including a ruler to estimate the size of the lesion, is recommended.

**Chest X-Ray.** Lesions on chest x-ray are acceptable as measurable lesions when they are clearly defined and surrounded by aerated lung. However, CT is preferable.

**Conventional CT and MRI.** This guideline has defined measurability of lesions on CT scan based on the assumption that CT slice thickness is 5 mm (0.5 cm) or less. If CT scans have slice thickness greater than 5 mm (0.5 cm), the minimum size for a measurable lesion should be twice the slice thickness. MRI is also acceptable in certain situations (e.g. for body scans).

Use of MRI remains a complex issue. MRI has excellent contrast, spatial, and temporal resolution; however, there are many image acquisition variables involved in MRI, which greatly impact image quality, lesion conspicuity, and measurement. Furthermore, the availability of MRI is variable globally. As with CT, if an MRI is performed, the technical specifications of the scanning sequences used should be optimized for the evaluation of the type and site of disease. Furthermore, as with CT, the modality used at follow-up should be the same as was used at baseline and the lesions should be measured/assessed on the same pulse sequence. It is beyond the scope of the RECIST guidelines to prescribe specific MRI pulse sequence parameters for all scanners, body parts, and diseases. Ideally, the same type of scanner should be used and the image acquisition protocol should be followed as closely as possible to prior scans. Body scans should be performed with breath-hold scanning techniques, if possible.

**PET-CT.** At present, the low dose or attenuation correction CT portion of a combined PET-CT is not always of optimal diagnostic CT quality for use with RECIST measurements. However, if the site can document that the CT performed as part of a PET-CT is of identical diagnostic quality to a diagnostic CT (with IV and oral contrast), then the CT portion of the PET-CT can be used for RECIST measurements and can be used interchangeably with conventional CT in accurately measuring cancer lesions over time. Note, however, that the PET portion of the CT introduces additional data which may bias an investigator if it is not routinely or serially performed.

**Ultrasound.** Ultrasound is not useful in assessment of lesion size and should not be used as a method of measurement. Ultrasound examinations cannot be reproduced in their entirety for independent review at a later date and, because they are operator dependent, it cannot be guaranteed that the same technique and measurements will be taken from one assessment to the next. If new lesions are identified by ultrasound in the course of the study, confirmation by CT or MRI is advised. If there is concern about radiation exposure at CT, MRI may be used instead of CT in selected instances.

**Endoscopy, Laparoscopy.** The utilization of these techniques for objective tumor evaluation is not advised. However, such techniques may be useful to confirm complete pathological response when biopsies are obtained or to determine relapse in trials where recurrence following complete response (CR) or surgical resection is an endpoint.

**Tumor Markers.** Tumor markers alone cannot be used to assess response. If markers are initially above the upper normal limit, they must normalize for a patient to be considered in complete clinical response. Specific guidelines for both CA-125 response (in recurrent ovarian cancer) and PSA response (in recurrent prostate cancer) have been published [JNCI 96:487-488, 2004; J Clin Oncol 17, 3461-3467, 1999; J Clin Oncol 26:1148-1159, 2008]. In addition, the Gynecologic Cancer Intergroup has developed CA-125 progression criteria which are to be integrated with objective tumor assessment for use in first-line trials in ovarian cancer [JNCI 92:1534-1535, 2000].

**Cytology, Histology.** These techniques can be used to differentiate between partial responses (PR) and complete responses (CR) in rare cases (e.g., residual lesions in tumor types, such as germ cell tumors, where known residual benign tumors can remain).

The cytological confirmation of the neoplastic origin of any effusion that appears or worsens during treatment when the measurable tumor has met criteria for response or stable disease is mandatory to differentiate between response or stable disease (an effusion may be a side effect of the treatment) and progressive disease.

**FDG-PET.** While FDG-PET response assessments need additional study, it is sometimes reasonable to incorporate the use of FDG-PET scanning to complement CT scanning in assessment of progression (particularly possible 'new' disease). New lesions on the basis of FDG-PET imaging can be identified according to the following algorithm:

- a. Negative FDG-PET at baseline, with a positive FDG-PET at follow-up is a sign of PD based on a new lesion.
- b. No FDG-PET at baseline and a positive FDG-PET at follow-up: If the positive FDG-PET at follow-up corresponds to a new site of disease confirmed by CT, this is PD. If the positive FDG-PET at follow-up is not confirmed as a new site of disease on CT, additional follow-up CT scans are needed to determine if there is truly progression occurring at that site (if so, the date of PD will be the date of the initial abnormal FDG-PET scan). If the positive FDG-PET at follow-up corresponds to a pre-existing site of disease on CT that is not progressing on the basis of the anatomic images, this is not PD.
- c. FDG-PET may be used to upgrade a response to a CR in a manner similar to a biopsy in cases where a residual radiographic abnormality is thought to represent fibrosis or scarring. The use of FDG-PET in this circumstance should be prospectively described in the protocol and supported by disease-specific medical literature for the indication. However, it must be acknowledged that both approaches may lead to false positive CR due to limitations of FDG-PET and biopsy resolution/sensitivity.

Note: A 'positive' FDG-PET scan lesion means one which is FDG avid with an uptake greater than twice that of the surrounding tissue on the attenuation corrected image.

